## **4 SUBJECT SELECTION AND WITHDRAWAL**

### **4.1 Inclusion Criteria**

- Admitted into the SICU/8100, CTICU/7100, or NMCCS 8100 or 9100
- Aged 18 years or older
- Mechanically ventilated
- Arterial line placed
- Vigileo/Flotrac System being used for guidance of fluid management

### **4.2 Exclusion Criteria**

- Pregnancy
- Prisoner status
- Extreme hemodynamic instability
- Multiple vasopressors in use with questionable peripheral blood flow
- Lack of appropriate sites for sensor placement
- Patient or patient's legal representative refusal

### **4.3 Subject Recruitment and Screening**

The SICU/8100, CTICU/7100 or NMCCS 8100 or 9100 patient census will be screened by the research team to identify the potential candidates. There will potentially be up to 600 patients participating at Loma Linda University in this study.

### **4.4 Informed Consent Process**

Study team members will approach the subject or subject's legally authorized representative to explain the study. Subject or subject's legally authorized representative will be informed about the potential benefits and risks of participation and informed that their participation is voluntary and their decision will not impact patient care. Subject or subject's legally authorized representative will be given adequate time to read the consent form and ask questions. Once the subject or subject's legally authorized representative have had all the questions answered and agreed to participate, the subject or subject's legally authorized representative will be asked to sign the informed consent form and HIPAA form.

## **5 STUDY DEVICES**

The Masimo Radical-7 is a noninvasive monitor that measures arterial oxygen saturation (SpO2), pulse rate (PR), and perfusion index (PI), along with optional measurements of hemoglobin (SpHb), carboxyhemoglobin (SpCO®), total oxygen content (SpOC), methemoglobin (SpMet), Pleth Variability Index (PVI®), Oxygen Reserve Index (ORI™), [REDACTED]

[REDACTED] Masimo SET® technology is clinically proven to satisfy all sensitivity and specificity requirements for pulse oximetry. Masimo rainbow® technology uses 7+ wavelengths of light to continuously and noninvasively measure carboxyhemoglobin (SpCO), methemoglobin (SpMet), and total hemoglobin (SpHb®), as well as providing a more reliable probe-off detection. Total oxygen content (SpOC) provides a calculated measurement of the amount of oxygen in arterial blood, which may provide useful information about oxygen both dissolved in plasma and combined with hemoglobin. Perfusion Index (PI) with trending capability indicates arterial pulse signal strength and may be used as a diagnostic tool during low perfusion. Pleth Variability Index (PVI) may show changes that reflect physiologic factors such as vascular tone, circulating blood volume, and intrathoracic pressure excursions. [The utility of PVI is unknown at this time and requires further clinical studies. Technical factors that may affect PVI include probe malposition and patient motion.] Oxygen Reserve Index (ORI) is an index measured noninvasively and continuously to provide an earlier indication of impending hypoxia by extending oxygen monitoring of pulse-oximetry to the moderate hyperoxic regions. [REDACTED]

[REDACTED]. A detailed description of the Masimo Radical-7 can be found in the attached manual. The syringes and sample tubes for the additional blood samples will be provided by Masimo.

Investigational devices to be used in this study are non-invasive prototype sensors similar in design, material, and risk to Masimo FDA-cleared products that may be placed on the fingers, hands, ears, forehead, nose (includes placement on or across alar, nasal cartilage, septum, etc), neck, toes, feet, and/or body, shielded from outside light, and attached to the Masimo Rainbow monitor. The energy output and materials used in the investigational sensors are similar to the FDA-cleared models and pose no additional risk to the subjects. Investigational sensors used in the study have been tested and shown to meet electrical, thermal conductivity, and biocompatibility safety standards. [REDACTED]

[REDACTED]

[REDACTED]

### **5.1 Device Accountability**

#### **5.1.1 Receipt of Study Device**

Upon receipt of the of the study device supplies, an inventory must be performed and the device accountability log filled out and signed by the person accepting the shipment. It is important that the designated study staff counts and verifies that the shipment contains all the items noted in the shipment inventory. Any damaged or unusable study devices in a given shipment will be documented in the study files. The investigator must notify the study sponsor of any damaged or unusable study devices that were supplied to the investigator's site.

#### **5.1.2 Use of Study Device**

Use of devices and sensors will be documented on case report forms for each subject.

### 5.1.3 Return or Destruction of Study Device

At the completion of the study, there will be a final reconciliation of study devices and sensors shipped, devices/sensors used, and devices/sensors remaining. This reconciliation will be logged on the device accountability log. Any discrepancies noted will be investigated, resolved, and documented prior to return or destruction of unused study devices. Devices destroyed on site will only be upon written instruction from the sponsor and will be documented in the study files.

## 6 STUDY PROCEDURES

### 6.1 Study Procedures

Routine monitors will be used such as pulse oximeter, blood pressure cuff, 5 lead EKG and additional monitors per discretion of the treating physician. Additionally, up to eight Masimo noninvasive sensors will be placed on the fingers, hands, ears, forehead, nose (includes placement on or across alar, nasal cartilages, septum, etc.), neck, toes, feet and/or body, shielded from outside light, and attached to the Masimo Rainbow monitor. Pulse oximeter sensors will be properly aligned to ensure that the emitter and the detector are across from each other. For the sensors placed on the cavity like ala or septum, the site will be cleared of any pre-existing mucus. A standard pulse oximetry sensor will be placed on an appropriate site and attached to the standard ICU monitor. An arterial catheter will be required for enrollment into the study. A study team member will record various measurements of heart rate, arterial blood pressure, cardiac output, SVV, PPV, PVI and PI, etc. from the different devices used for comparison. High speed arterial waveform data will be electronically collected from the arterial line using data acquisition system. Ventilator waveform data may be collected from the ventilator box.

### 6.2 Study Duration

Patients admitted directly into SICU/8100, CTICU/7100 or NMCCS 8100 or 9100 may be monitored for up to three days.

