**DORO0001 version 1**

It may be that continuous Hb assessment could allow more accurate titration of blood transfusion to maintain Hb levels in a target range. This may result in limiting the total number of units transfused to a patient, the amount of time a patient's Hb level is above or below the target range, and the amount of blood draws for Hb lab checks.

[REDACTED] This information can be characterized as the Oxygen Reserve Index (ORI). This index is presented on a unit-less scale between 0 and 1 that correlates with arterial oxygen concentrations between 100 and 200mmHg. This index is designed to supplement standard arterial hemoglobin saturation monitoring. (12) Preliminary studies have evaluated the relationship between ORI and paO2 in the general surgical population. (11) In addition, the ORI has been demonstrated to provide a clinically useful advanced warning of impending arterial hemoglobin desaturation in pediatric patients. (13) The relationship between ORI and standard saturation monitoring is characterized by this illustration from the above referenced whitepaper:

Oxygen Reserve Index (ORI) is an index measured noninvasively and continuously to provide an earlier indication of impending hypoxia by extending oxygen monitoring of pulse-oximetry to the moderate hyperoxic (100-200 mmHg) regions.

The device also has the capability to continuously measure the plethysmography variability index (PVI). PVI is calculated automatically and represents the variation in amplitude of the pulse oximeter waveform with respiration (22-24). PVI is analogous to stroke volume variation (SVV), which may be derived from arterial waveform, pulmonary artery catheter, esophageal Doppler, echocardiography or other device measured variations with respiration [REDACTED]

[REDACTED] Of course use of this device requires an arterial catheter be placed. Multiple studies have demonstrated that SVV is a valuable tool in predicting fluid responsiveness in mechanically ventilated patients. When SVV is elevated, patients are more likely to respond with increased stroke volume and cardiac output when fluid is administered. The threshold SVV of

---

**Validation of a pulse oximetry based hemoglobin measurement system. Comparison of plethysmographic variability index to standard methods of guiding fluid and transfusion management in the critically ill adult patients. Validation of Clinical Efficacy of ORI for supplemental oxygen titration.**

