## **2 STUDY DESIGN**

This is a sponsored, prospective, nonrandomized, sequential data collection study to be performed in anemic adult patients who are admitted into the Surgical Intensive Care Unit (SICU/8100), Cardiothoracic Intensive Care Unit (CTICU/7100) or Neuro-Multidisciplinary Critical Care Services (NMCCS 8100 or 9100). Noninvasive pulse oximetry-determined SpHb will be compared to ABG co-oximetry and research lab equipment-determined Hb values, Oxygen Reserve Index (ORI) will be correlated with paO2 via ABG, PVI and acoustic waveform data will be compared to the arterial waveform extracted SVV or PPV values. The study goal is to establish the correlation of Hb values determined by the SpHb system with Hb as measured by other validated devices, use ORI to correlate with paO2 in the moderate hyperoxic regions and correlation of PVI with SVV or PPV values.

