### 6.4 Data Collection

Additional data collection for this study will include demographics such as age, height, weight, [REDACTED] (skin tone), site dimensions (e.g. finger diameter for finger sensor, alar thickness for nose sensor), pre-existing comorbidities, surgical procedures performed [REDACTED] and ASA status, medications. Volumes of fluid input (blood, albumin, crystalloid) and output (estimated blood loss, urine output) will also be recorded. Other de-identified data such as ventilator settings, may be collected for data analysis. Hospital records, clinical and office charts, laboratory notes, memoranda, recorded data from automated instruments, and copies or transcriptions certified after verification as being accurate and complete may be accessed to obtain above defined data.

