### 6.5 Data Analysis

Statistical analyses will be performed using statistical analysis software to determine the correlation between changing hemoglobin concentrations determined by the 3 different methods and spectral absorbance. ORI data will also be analyzed to determine any correlation with PaO2 obtained by ABG. PVI data will be correlated to SVV. Outcome data will be analyzed for any relationships between the inciting event, blood loss and outcome markers to evaluate for any predictive value of inciting factors and any correlation between transfusion and fluid management variables on outcome.

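### Section 6.5 pools PVI-SVV pairs regardless of ventilation status, and recording that status is optional, so pairs from weaning or after extubation can bias the correlation in either direction

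*Combined protocol and SAP*

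**What the plan says.** - **Entry.** Section 4.1 lists "Mechanically ventilated", an arterial line, and "Vigileo/Flotrac System being used for guidance of fluid management" as inclusion criteria. No section reviewed requires any of the three to continue after enrolment.
- **Duration.** Under Section 6.2, patients "may be monitored for up to three days". This is a maximum and is not tied to ventilation.
- **Support for the reference.** Section 1.1 states: "Multiple studies have demonstrated that SVV is a valuable tool in predicting fluid responsiveness in mechanically ventilated patients". Its argument about adding PEEP concerns the same patients.
- **Analysis.** Section 2 gives the PVI goal as "correlation of PVI with SVV or PPV values". Section 6.5 reduces this to "PVI data will be correlated to SVV". Neither section limits, flags or stratifies pairs by ventilation status.
- **Ventilator data.** Section 6.4: "Other de-identified data such as ventilator settings, may be collected for data analysis". Section 6.1 makes the ventilator waveform optional in the same way.

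**The concern.** Section 1.1 names weaning and extubation as a central problem in this population, and ORI is studied partly for that reason. Following patients through weaning therefore fits the study's own aims. If PVI and SVV are still recorded at that stage, Section 6.5 as written gives no ground for leaving those pairs out.

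The PVI result would then mix two kinds of pair: those taken where the protocol supports its reference, and those taken where it states no support. The mix would depend on how quickly patients come off the ventilator and how long their lines stay in, not on the sensor. A reader could not tell whether a given correlation reflects PVI or that mix. If ventilation status was not captured with each pair, the analyst may be unable to separate the two kinds afterwards.

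**Working it through.** The plan gives no expected correlation, SD, power or sample-size derivation for PVI, only a ceiling of 600 patients (Section 4.3). There is no figure to reproduce. What follows is a sensitivity check, and every input except the three-day window is an assumption.

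**Step 1: share of one patient's pairs taken off the ventilator.** Three days is 72 h. With evenly spaced pairs over the full window, extubation at hour h, and the SVV source still in use, the share is 1 − h/72:
- h = 24: 1 − 24/72 = 67%
- h = 48: 1 − 48/72 = 33%
- h = 60: 1 − 60/72 = 17%

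The share f across the whole study is unknown, because the documents give no extubation times.

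**Step 2: pooled correlation.** Let r1 and r2 be the correlations on and off the ventilator. Off the ventilator, let both indices have SD s times larger and a mean shifted by d (in on-ventilator SDs). Then:

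pooled r = [(1−f)·r1 + f·r2·s² + f(1−f)·d²] / [(1−f) + f·s² + f(1−f)·d²]

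With r1 = 0.70:

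| Assumption off the ventilator | f = 10% | 20% | 33% | 50% |
|---|---|---|---|---|
| r2 = 0, equal means and SDs | 0.63 | 0.56 | 0.47 | 0.35 |
| r2 = 0.30, equal means and SDs | 0.66 | 0.62 | 0.57 | 0.50 |
| r2 = 0, SDs 1.5 times larger | 0.56 | 0.45 | 0.33 | 0.22 |
| r2 = 0, both means shift 2 SD | 0.73 | 0.73 | 0.72 | 0.68 |
| r2 = 0.30, both means shift 2 SD | 0.75 | 0.77 | 0.77 | 0.75 |

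Worked entries at f = 20%:
- No shift, r2 = 0: 0.8 × 0.70 = 0.56.
- 2 SD shift, r2 = 0: (0.56 + 0.16 × 4) / (1 + 0.16 × 4) = 1.20/1.64 = 0.73.
- 2 SD shift, r2 = 0.30: (0.56 + 0.06 + 0.64) / 1.64 = 1.26/1.64 = 0.77.

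**Step 3: where the direction turns.** At f = 20% and r2 = 0, pooled r equals 0.70 when 0.56 + 0.16d² = 0.70(1 + 0.16d²). That gives d² = 0.14/0.048 = 2.92, so d is about 1.7. A smaller shared shift lowers the correlation and a larger one raises it.

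**Step 4: after restriction.** Limiting the analysis to on-ventilator pairs returns r1 by construction, whatever f, r2, s and d are.

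**The case against.** Four parts of the opposing case have weight.

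1. **Off-ventilator pairs are not documented.** A reader might infer that pairs after extubation will enter the correlation. The documents do not say so. Three days is a ceiling, and a pair needs the arterial line, and FloTrac for its SVV, still in use. Nothing says that either continues. This stands, so the point is that such pairs can enter. The limit is partial, because Section 6.1 collects the arterial waveform electronically and Section 2 refers to SVV or PPV extracted from it, so the source can remain wherever the line does.

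2. **Attenuation is not established.** A reader might infer that pooling makes PVI look worse. Section 1.1 supports SVV as a predictor of fluid responsiveness, whereas the study correlates PVI with SVV. Losing the first does not show that the two indices stop moving together, and Section 1.1 calls them analogous. This also stands: a shared shift can raise the pooled correlation. What remains is bias of unknown direction and a result that is hard to interpret.

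3. **Status might be recovered later.** Section 6.4 allows access to charts and automated instrument records, so it would be too strong to say that the pairs cannot be identified. The route is possible but not assured. Sponsor engineers analyse the data (Section 6.6) and receive them de-identified (Section 10.1), so a status not captured with each pair may never reach them.

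4. **The reason for the entry criterion is not given.** It is tempting to read the ventilation criterion as chosen to protect SVV. Section 4.1 gives no reason, and the weaning and ORI rationale could explain it equally well.

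The three-day window is not itself the defect, since it also serves SpHb and ORI. The gap lies in Section 6.5 and in the optional data of Sections 6.1 and 6.4. Section 3 was not in the text reviewed, so a restriction there cannot be excluded. Sections 6.2 to 6.5, where such a rule would operate, contain none.

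**Conclusion.** The gap is real and should be closed. The PVI-SVV correlation has no restriction by ventilation status, and the data needed to apply one later are optional. I am confident of that from the text, subject to Section 3.

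The size and direction of the effect are not known. The illustration assumes r = 0.70 on the ventilator and invented values for everything else. It runs from 0.22 (half the pairs off the ventilator, no association, wider spread) to 0.77 (20% or 33% off, r = 0.30, shared 2 SD shift). It shows that the pooled figure can move materially either way for reasons unrelated to the device. It does not predict the trial's result. SpHb and ORI are outside this point.

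**What to change.** **Section 6.4:** make ventilation status and mode (controlled, assisted or spontaneous, extubated) a mandatory field at each recorded PVI/SVV/PPV time, in place of optional collection.

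**Section 6.5:** base the main PVI versus SVV/PPV analysis on pairs taken during controlled mechanical ventilation. Report assisted or spontaneous pairs and post-extubation pairs separately, as exploratory. Restricting to ventilated pairs without naming the mode would not be enough, because it could keep supported spontaneous breathing during weaning in the main analysis.

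Leave SpHb and ORI collection as it is.

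**Cost:** one field per time point, which should normally be available from the ICU chart, and a sentence or two in Section 6.5. The main PVI analysis will have fewer pairs, although the rest remain reportable. No patients, procedures or changes in care are added.

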### 6.3 Sample Collection

Each patient enrolled in this trial will have Hb measured and recorded prior to data collection. SpHb data will be obtained continuously or via spot check in SICU/8100, CTICU/7100 or NMCCS 8100 or 9100. During spot checks, blood samples must be obtained simultaneously with noninvasive reading and will thus be coordinated. SpHb will be recorded with each blood draw sample. Additional blood sampling is necessary to validate the SpHb system. For patients over 15 kg weight, at each standard of care ABG sampling an additional 4 mL of blood will be collected for patients in the SICU/8100, CTICU/7100 or NMCCS 8100 or 9100 and sent for cell count and cyanomethemoglobin determination by Masimo laboratories. These additional samples will be obtained to a maximum of 10 ABG samples per patient, only when ordered by ICU team. Thus up to 40 mL total additional blood volume may be obtained in one subject. Blood samples will be inverted or rolled 10 times to ensure proper mixing to prevent micro clotting. Patients less than 15 kg will not have any additional blood sampling done at the time of ABG analysis. All decisions regarding fluid management and the need for transfusion will be at the discretion of the attending physicians caring for the patient and will be based on the results of the clinical status and Hb measured by CBC as is customary for transfusion. The time of the CBC draw and corresponding blood samples will be noted as part of the data collection for validation of the system.

### 6.4 Data Collection

Additional data collection for this study will include demographics such as age, height, weight, [REDACTED] (skin tone), site dimensions (e.g. finger diameter for finger sensor, alar thickness for nose sensor), pre-existing comorbidities, surgical procedures performed [REDACTED] and ASA status, medications. Volumes of fluid input (blood, albumin, crystalloid) and output (estimated blood loss, urine output) will also be recorded. Other de-identified data such as ventilator settings, may be collected for data analysis. Hospital records, clinical and office charts, laboratory notes, memoranda, recorded data from automated instruments, and copies or transcriptions certified after verification as being accurate and complete may be accessed to obtain above defined data.

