## **1.2 Study Devices**

The Masimo Radical-7 is a noninvasive monitor that measures arterial oxygen saturation (SpO2), pulse rate (PR), and perfusion index (PI), along with optional measurements of hemoglobin (SpHb), carboxyhemoglobin (SpCO®), total oxygen content (SpOC), methemoglobin (SpMet), Pleth Variability Index (PVI®), Oxygen Reserve Index (ORI™), Acoustic Respiration Rate (RRa®), and Pleth Respiration Rate (RRp). Masimo SET® technology is clinically proven to satisfy all sensitivity and specificity requirements for pulse oximetry. Masimo rainbow® technology uses 7+ wavelengths of light to continuously and noninvasively measure carboxyhemoglobin (SpCO), methemoglobin (SpMet), and total hemoglobin (SpHb®), as well as providing a more reliable probe-off detection. Total oxygen content (SpOC) provides a calculated measurement of the amount of oxygen in arterial blood, which may provide useful information about oxygen both dissolved in plasma and combined with hemoglobin. Perfusion Index (PI) with trending capability indicates arterial pulse signal strength and may be used as a diagnostic tool during low perfusion. Pleth Variability Index (PVI) may show changes that reflect physiologic factors such as vascular tone, circulating blood volume, and intrathoracic pressure excursions. [The utility of PVI is unknown at this time and requires further clinical studies. Technical factors that may affect PVI include probe malposition and patient motion.] Oxygen Reserve Index (ORI) is an index measured noninvasively and continuously to provide an earlier indication of impending hypoxia by extending oxygen monitoring of pulse-oximetry to the moderate hyperoxic regions. Respiration rate can be determined by the acoustic (RRa) or plethysmographic waveform (RRp). [REDACTED]

FastSat® tracks rapid changes in arterial O2. A detailed description of the Masimo Radical-7 can be found in the attached manual.

Masimo Rainbow sensors: a finger probe that consists of a series of light emitting diodes (LEDs) and photodetectors. First, light is emitted through a capillary bed; then, the sensors detect the transmitted light. The signals from the sensor are processed and used to quantify hemoglobin levels noninvasively.

Data acquisition system: consists of a hardware component connected to a laptop with data collection software used to capture wavelength data.

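### Skin tone and sensor-site dimensions are collected, but no correlation in Section 6.5 uses them, and a correlation says little about an offset confined to one group

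*Combined protocol and SAP*

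**What the plan says.** Section 1.2 explains how the sensor works: "First, light is emitted through a capillary bed; then, the sensors detect the transmitted light". The detected signal is then converted to a hemoglobin value. Section 6.4 lists among the data to be collected "skin tone), site dimensions (e.g. finger diameter for finger sensor, alar thickness for nose sensor". The word before skin tone is redacted, so the measurement scale is not visible.

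Section 6.5 shows no redaction and contains four analyses:

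- Hb: "determine the correlation between changing hemoglobin concentrations determined by the 3 different methods and spectral absorbance".
- ORI: "ORI data will also be analyzed to determine any correlation with PaO" (PaO2, from the ABG).
- PVI: "PVI data will be correlated to SVV".
- Outcomes: "Outcome data will be analyzed for any relationships between the inciting event, blood loss and outcome markers", together with transfusion and fluid variables.

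None of these names skin tone, finger diameter or alar thickness as a stratum, covariate or effect modifier. Section 2 frames the aim the same way, as being to "establish the correlation of Hb values determined by the SpHb system with Hb as measured by other validated devices". The nearest related idea is at the end of Section 1.1, which proposes comparing fluid-status measurements across sources and sites. That concerns where a sensor sits, not how thick the tissue is there or what the skin tone is.

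**The concern.** A transmitted-light device may read differently through darker skin or thicker tissue, and the protocol already collects both features. Site dimension is even specified by sensor type, so it is more than a routine demographic. Yet the plan as written ends in correlation coefficients, which measure how tightly two series move together and not whether one is shifted. A shift in a minority of patients adds only a little scatter, so the coefficient hardly moves.

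What is at stake is the later use of the result. Section 1.3 gives as a possible future benefit that the system might prove accurate enough to replace invasive Hb or PaO2 measurement in critically ill adults. That is a statement about individual readings in all such patients. A good overall coefficient could be taken to support it while one identifiable group is read with an offset.

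Planning in advance also matters for a practical reason. Under Section 6.6 the sponsor's engineers analyze the data and the site department receives aggregate data. Unless by-group results are planned, the site may be unable to produce them later.

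**Working it through.** **Figures in the documents.** The only sample-size figure is the ceiling of 600 patients in Section 4.3. It comes with no SD, expected correlation, accuracy limit, alpha or power, so there is nothing to reproduce. Section 6.3 allows up to 10 additional research samples per patient.

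**Assumptions, none from the documents.** Device error SD e = 1.0 g/dL; Hb SD s = 1.0 to 2.0 g/dL; share of readings in the affected group p = 10% to 30%; group bias b = 1.0 g/dL, with 2.0 g/dL as a check; group membership independent of Hb.

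**Step 1: effect on the correlation.** With SpHb = Hb + error + b for readings in the group, r = s / √(s² + e² + p(1−p)b²). The overall mean bias is p × b.

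Worked case, s = 1.5, p = 0.15, b = 1.0:

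- no group bias: r = 1.5 / √(2.25 + 1.00) = 0.832
- with group bias: r = 1.5 / √(2.25 + 1.00 + 0.1275) = 0.816
- overall mean bias: 0.15 × 1.0 = 0.15 g/dL, against 1.0 g/dL in the group.

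Range for b = 1.0 g/dL:

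| Hb SD | Share | r, no bias | r, with bias | Drop |
|---|---|---|---|---|
| 1.0 | 10% | 0.707 | 0.692 | 0.015 |
| 1.0 | 30% | 0.707 | 0.673 | 0.034 |
| 1.5 | 15% | 0.832 | 0.816 | 0.016 |
| 2.0 | 10% | 0.894 | 0.886 | 0.008 |
| 2.0 | 30% | 0.894 | 0.876 | 0.018 |

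The drop runs from 0.008 to 0.034. For b = 2.0 g/dL it is 0.031 to 0.092 at shares of 10% to 20%, and up to 0.114 at 30%. A drop of that size could be noticed, but without a by-group analysis it could not be traced to skin tone or site size. The plan also sets no target r against which to judge it.

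**Step 2: would an overall agreement analysis be enough?** In the worked case the SD of the differences is √(1.00 + 0.1275) = 1.06. The overall limits are 0.15 ± 1.96 × 1.06, about −1.93 to 2.23 g/dL, against ±1.96 with no group bias. Inside the group they are 1.0 ± 1.96, or −0.96 to 2.96. Overall limits move little as well, so the breakdown by group is needed in addition.

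**Step 3: precision of a by-group result.** With one reading per patient and N patients, the 95% half-width for the difference in bias is 1.96 × e × √(1/(Np) + 1/(N(1−p))).

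- N = 600, p = 10%: 1.96 × √(1/60 + 1/540) = 0.27; p = 20%: 1.96 × √(1/120 + 1/480) = 0.20 g/dL.
- N = 100, p = 10%: 1.96 × √(1/10 + 1/90) = 0.65; p = 20%: 1.96 × √(1/20 + 1/80) = 0.49 g/dL.

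At two-sided alpha 0.05, power for a 1.0 g/dL difference is above 0.99 at 600 patients and 0.85 to 0.98 at 100. For 0.5 g/dL it is 0.96 to 0.998 at 600 and 0.32 to 0.52 at 100. Repeated readings would change these figures.

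**The case against.** The strongest reply is that the real gap is elsewhere. A correlation ignores any constant offset, including one shared by every reading, and Section 6.5 plans no measure of bias or agreement at all. Without one there is nothing to break down by skin tone. This is right as far as it goes, and it is why the fix starts with an agreement analysis. Step 2 shows that such an analysis, if reported only overall, would still leave a group offset largely out of sight.

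Second, the Hb sentence in 6.5 speaks of changing concentrations and spectral absorbance. If it means within-patient change, a fixed group offset cancels and the r values above do not describe the planned analysis. That is fair, but under that reading the analysis would be blind to the offset altogether.

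Third, collecting covariates for description is ordinary, and age, height, weight and medications also have no named use in the device correlations. That is true. Skin tone and site dimension differ in that they bear directly on the optical measurement.

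Fourth, the section between 2 and 4 was not in the text available for review, and other passages are redacted. A use stated only there cannot be excluded.

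Several stronger readings are tempting and are not supported:

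- *That the device is biased by skin tone or finger size.* No document says so. Section 1.2 mentions only probe malposition and motion, and only for PVI.
- *That 6.5 commits to one pooled coefficient.* It never says pooled and plans three device correlations. Pooling is inferred from the absence of any stratum.
- *That the study is sure to detect a group offset.* The 600 is a ceiling, no minimum group size is set, and up to eight sensors at varied sites (Section 6.1) may thin the data per sensor type.
- *That participants could be treated on a wrong SpHb value.* Section 6.3 bases transfusion and fluid decisions on clinical status and CBC Hb.

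**Conclusion.** The point holds as a gap in the analysis plan. Two variables in the optical path are collected, the correlations in 6.5 use neither, and a correlation is a poor instrument for showing an offset in a minority of patients. Under the stated assumptions a 1.0 g/dL group bias costs 0.008 to 0.034 in r. The SDs, shares and biases are illustrative, and the argument does not depend on such a bias being present: the plan as written would not show whether it is. By-group estimates would be reasonably precise near the 600 ceiling and wide at 100 patients. The change should be made before the data are analyzed. It bears on what may later be claimed for the device, not on the care of participants.

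**What to change.** In Section 6.5:

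- Add an agreement analysis of SpHb minus reference Hb with a patient random effect for the repeated samples. Fit it separately by sensor type, with skin tone (on the scale collected) and that sensor's own site dimension as terms: finger diameter for finger sensors, alar thickness for nose sensors.
- Report bias and limits of agreement with 95% intervals, overall and by skin-tone group.
- Examine the ORI-PaO2 relation with the same terms. ORI is a unitless index, so a simple difference from PaO2 has no meaning.
- Label the group results as prespecified estimates, report the number of patients in each group, and say that small groups will be imprecise.

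Do not add a rule confining the accuracy claim to groups in which it holds unless an accuracy limit is set in advance. Without one, groups would be picked after the results are seen.

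The variables are already collected, so no new patients or procedures are needed. The cost is modest extra analysis and wide intervals in small groups. Securing a minimum number per skin-tone group would be a further decision, affecting enrollment.
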